#### 330 **2.3 Screening Visit**

- After the ICF has been signed, a potential participant will be evaluated for study eligibility
- through the elicitation of a medical history, performance of ophthalmic tests as described below,
- and genetic testing, if applicable. The Screening Visit date will be the date the Screening Visit
- testing procedures started. All Screening Visit testing procedures will be completed on this date.

## **2.3.1 Eligibility Criteria**

- To be eligible to **enroll into the genetic screening phase,** a study participant must meet all the inclusion criteria and none of the exclusion criteria at the Screening Visit.
- 338 **2.3.1.1 Participant Inclusion Criteria**
- Participants must meet all the following inclusion criteria at the Screening Visit to be eligible to
   enroll into the genetic screening phase.
- 1. Willing to participate in the study and able to communicate consent during the 341 consent process. 342 2. Willing and able to complete all study visit assessments at each visit over the forty-343 eight (48) month study period. 344 **3.** Age  $\geq$  12 years 345 4. Adult participants must have the capacity to consent on their own behalf. 346 5. Must meet one (1) of the Genetic Screening Criteria below: 347 At least 2 disease-causing variants in the OAT gene which are 348 homozygous or heterozygous in trans, based on a report from a 349 clinically certified lab, or a report from a research lab that has been pre-350 approved by the study Genetics Committee. 351 352 **O**R 353

354	
355	• At least 2 disease-causing variants in the OAT gene with unknown
356	phase, based on a report from a clinically certified lab, or a report from a
357	research lab that has been pre-approved by the study Genetics Committee,
358	AND must meet both of the following phenotype criteria:
359	1. Classic fundus appearance of gyrate atrophy (based on
360	investigator discretion) AND
361	2. Elevated ornithine levels $>300 \mu mol/L$ (documented on any
362	prior lab report).
363	2.3.1.2 Ocular Inclusion Criteria
364	Participant must meet the following criteria at the Screening Visit to enroll into the genetic
365	screening phase.
366	6. Both eyes must have a clinical diagnosis of retinal dystrophy
367	7. Both eyes must permit good quality photographic imaging (for example, but not
368	limited to, clear ocular media, adequate pupil dilation, stable fixation).
369	2.3.1.3 Participant Exclusion Criteria
370	Participants must not meet any of the following exclusion criteria at the Screening Visit to be
371	eligible to enroll into the genetic screening phase.
372	1. Single pathogenic or likely pathogenic genetic variants known to be associated with
373	autosomal dominant retinitis pigmentosa/retinal dystrophy (AD, heterozygous), X-
374	linked retinitis pigmentosa/retinal dystrophy (XL, hemizygous), or mitochondrial
375	inheritance.
376	2. Expected to enter experimental treatment trial at any time during this study.
377	3. History of more than one (1) year of cumulative treatment, at any time, with an agent
378	associated with pigmentary retinopathy, including amiodarone, chloroquine,
379	deferoxamine, hydroxychloroquine, pentosan polysulfate, tamoxifen, and deferoxamine.
380	
381	Note: Since this is a Natural History Study collecting data on the progression of GA, pregnant
382	women will not be specifically excluded from participation.
383	2.3.1.4 Ocular Exclusion Criteria
384	If either eye has any of the following ocular exclusion criteria at the Screening Visit, then the
385	participant is not eligible to enroll into the genetic screening phase.
386	4. Current vitreous hemorrhage.
387	5. Current complications of pathological myopia (for example, but not limited to,
388	myopic maculopathy including atrophy, scar, choroidal neovascularization, schisis)
389	that could inhibit imaging studies of gyrate atrophy-related chorioretinal degeneration
390	or assessment of visual function.
391	6. History of intraocular surgery (for example, but not limited to cataract surgery,
392	vitrectomy, penetrating keratoplasty, or LASIK) within the last 3 months.

393	7.	Current or any history of confirmed diagnosis of glaucoma (for example, but not
394		limited to glaucomatous VF changes or nerve changes, or history of glaucoma
395		filtering surgery).
396	8.	Current or any history of retinal vascular occlusion or proliferative diabetic
397		retinopathy.
398	9.	Any clinically significant cystoid macular edema, as determined by the Investigator,
399		that is not stable three (3) months before screening; use of chronic, prophylactic
400		treatment with topical or oral agents (for example, but not limited to, dorzolamide) is
401		allowed.
402	10	History or current evidence of ocular disease that, in the opinion of the investigator,
403		may confound assessment of visual function (for example, but not limited to,
404		tractional or rhegmatogenous retinal detachment, any vitreoretinal surgery, retinal
405		vascular occlusion, proliferative diabetic retinopathy).
406	11	. The following medications and treatments are prohibited as they can affect
407		progression of retinitis pigmentosa or confound the assessments. The participant must
408		not have received or plan to receive the following treatments.
409		i. Any use of ocular stem cell or gene therapy:
410		ii. Any treatment with ocriplasmin.
411		iii. Treatment with Ozurdex (dexamethasone), Iluvien or Yutiq (fluocinolone
412	10	acetonide) intravitreal implant.
413	12	The following medications and treatments are excluded within the specified
414		timeframe:
415		i. Treatment with an ophthalmic oligonucleotide within the last 9 months (last
416		treatment date is less than 9 months prior to Screening Visit date).
417		ii. Treatment with any other product for retinal dystrophy within five times the
418		expected half-life of the product (time from last treatment date to Screening
419		Visit date is at least 5 times the half-life of the given product).
420		iii. Treatment that can alter VA between Screening and Baseline (e.g.,
421		periorbital injections.
422	2.3.2 §	Screening Data Collection and Testing
423	Please refe	erence the schematic of study design at the beginning of the protocol for the flow of the
424		procedures. The following procedures will be performed at the Screening Visit. The
425	•	ocedures are detailed in the GYROS Clinical Site Manual of Procedures. An
426	01	of the equipment and technician requirements for all testing is in Chapter 5.1 Study
427		e Requirements. All ocular testing will be performed in each eye, right eye (OD) first
428	and then le	eft eye (OS). Screening procedures will last approximately four (4) hours.
429		
430	Participan	ts meeting criteria to continue will be enrolled into the genetic screening phase .
431	Otherwise	, the participant will be an initial screen failure .
432		
433	The follow	ving procedures will be performed, data collected, eligibility criteria checked, and
434	documente	ed at the Screening Visit.
435	1. Inc	clusion and exclusion criteria assessed
436	2. De	mographics: date of birth, sex, race, and ethnicity

437	3.	Contact information: this will be retained at the site and not entered on the study database
438 439 440	4.	Medical history: will be elicited from the study participant and extracted from available medical records, including patient-reported daily activities, pre-existing medical conditions, and medications.
441 442		• Participant will sign a release of medical information form to collect medical records and laboratory records.
443	5.	Concomitant medications
444 445 446	6.	Genetic screening assessment, including number and phase of mutations in the OAT gene, history of consanguinity, and collection of the source genetic report(s) available at the clinical site.
447 448 449 450		• This includes an assessment that the participant meets one of the Genetic Screening Criteria. If the participant does not meet the criteria for one of the Genetic Screening Criteria , then the remainder of procedures and testing are not required. The participant will be discontinued as an initial screen failure .
451	7.	Complete ophthalmic examination to include:
452		Slit lamp biomicroscopy
453		
 
Indirect ophthalmoscopy
 

454	8.	IOP
455		• IOP measurements will be taken prior to pupil dilation.
456	9.	VA (including refraction, ETDRS, BRVT if needed, LLVA if needed).
457 458		• The VA letter score will determine whether LLVA or BRVT will be performed. The criteria are defined in the GYROS Clinical Site Manual of Procedures.
459	10	Kinetic VF III4e
460 461 462 463 464 465		
 
Vision Cohort 1 and 2: Historical measurement performed within the last eighteen (18) months prior to the Screening Visit. If a historical measurement is not available, then perform the Kinetic VF III4e at the Screening Visit.
 
Vision Cohort 3: Collect the most recent historical measurement prior to the Screening Visit, if available. Kinetic VF III4e does not need to be performed at screening if a historical measurement is not available.
 

466	11.	Determination of Vision Cohort
467 468 469		• If the participant's determined Vision Cohort is closed for enrollment, the remainder of procedures and testing are not required. Participant will be discontinued as an initial screen failure .
470	12	Sample Collection
471		• The Site Personnel will collect one (1) fasting plasma sample.

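### Exclusion item 12.ii: the parenthesis describes the opposite time window from the sentence it annotates

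*Protocol*

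**What the plan says.** Section 2.3.1.4 of the protocol lists ocular exclusions. Its lead-in makes any listed item disqualifying: "If either eye has any of the following ocular exclusion criteria at the Screening Visit, then the" "participant is not eligible to enroll into the genetic screening phase". The stem of item 12 sets up a group of time-limited exclusions: "The following medications and treatments are excluded within the specified" timeframe.

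Two of the sub-items consist of a sentence followed by a clarifying parenthesis:

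- **12.i:** "Treatment with an ophthalmic oligonucleotide within the last 9 months (last" "treatment date is less than 9 months prior to Screening Visit date").
- **12.ii:** "Treatment with any other product for retinal dystrophy within five times the" "expected half-life of the product (time from last treatment date to Screening" "Visit date is at least 5 times the half-life of the given product").

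Nothing else in the protocol restates the half-life rule. Section 7.2.1 covers prohibited treatments during the study and contains no half-life condition.

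**The concern.** A parenthesis in an eligibility item normally tells the site how to apply the sentence. In 12.ii it points the other way: the sentence captures patients treated recently relative to the product's half-life, and the parenthesis captures patients treated long enough ago. Both stand inside a list where meeting the condition makes a candidate ineligible.

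What is at stake is whether site staff and monitors can apply and verify the criterion in one way. Section 2.1 plans approximately twelve sites worldwide. Section 9.3 names participant eligibility, together with adverse events, as the data that matter most for site monitoring. A criterion whose two halves disagree cannot be checked unambiguously against a patient's record.

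**Working it through.** No sample size, power or error-rate figure is involved, so the check is one of logic. Let *t* be the time from last treatment to the Screening Visit and *H* the half-life of the product.

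| Item | Sentence excludes | Parenthesis describes | Same patients? |
|---|---|---|---|
| 12.i | *t* within 9 months | *t* < 9 months | Yes |
| 12.ii | *t* within 5*H* | *t* ≥ 5*H* | No |

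**Direction of the list.** The lead-in to 2.3.1.4 and the stem of item 12 both make the described condition an exclusion. The sentence of 12.ii fits that frame. Its parenthesis fits only if it is taken as the condition for passing, and the text does not say so.

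**Worked cases for 12.ii, each half taken literally as the exclusion condition.**

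- *t* = 2*H*: excluded by the sentence, not excluded by the parenthesis.
- *t* = 10*H*: not excluded by the sentence, excluded by the parenthesis.
- *t* = 5*H* exactly: excluded by the parenthesis, and also by the sentence if its window includes the boundary. This is the only point where the two could agree.

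Apart from that boundary the two sets do not overlap, and together they cover every value of *t*. If both halves were applied as exclusions, anyone ever treated with such a product would be barred.

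**Scope.** Item 12.ii covers only products for retinal dystrophy not named elsewhere. Stem cell and gene therapy, ocriplasmin and the named intravitreal implants fall under item 11, and oligonucleotides under 12.i. Those items are unaffected.

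**Text damage.** The words that set the direction of the parenthesis are intact in the extracted text, so broken lines do not explain the mismatch.

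**The case against.** The strongest reply is that the direction can be recovered. The lead-in, the stem of item 12 and the sentence of 12.ii all agree; only the parenthesis differs. If the parenthesis is taken as the washout that a candidate must have completed, all four agree, and the defect is a passing condition written inside an exclusion item. That is a plausible account, and many sites would probably read it so. It lowers the seriousness of the point. It does not remove it, because the text does not mark the parenthesis as a passing condition and 12.i, directly above, uses the opposite convention.

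A reader might infer more than the protocol supports:

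- **That every previously treated candidate is caught.** Only those treated with a 12.ii product are. Nor does escaping one half admit anyone, since all other criteria still apply.
- **That sites will enrol opposite groups.** This would require a site to set aside the stem and the sentence in favour of the parenthesis. Nothing in the protocol shows that any site would. The monitoring focus on eligibility in section 9.3 also makes unnoticed divergence less likely, though it does not repair the wording.
- **That the parenthesis is what is programmed.** The eligibility form is not among the documents, and the protocol gives the parenthesis no precedence.
- **That the progression estimates would shift.** One participant is 1/45, about 2%, of the enrolment goal, but that is only the weight of one person. The protocol gives no count of candidates exposed to such products and no evidence on how exposure would affect progression.

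**Conclusion.** Wrong as written, and minor. The sentence and the parenthesis of item 12.ii describe complementary windows, and no other section resolves the conflict. The conclusion rests on the wording alone and on reading the parenthesis, as in 12.i, as a restatement of the exclusion. The number of candidates affected is not given, is probably small and could be zero. No sample size, precision or analysis figure depends on it. It is an internal inconsistency in an eligibility criterion; no design decision is disputed.

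**What to change.** The sponsor should reconcile the two halves of 12.ii so that the sentence and the parenthesis describe the same excluded patient, as 12.i already does. Which window applies is for the sponsor to state. The sponsor should also confirm that the eligibility form and any check built on it match the reconciled text; this is a precaution, since the form has not been seen. The cost is a one-line protocol clarification and a short review of the form.

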#### 472 **2.3.3 Initial Screen Failures**

473 Participants who do not meet criteria to continue as noted above will be discontinued as an

initial screen failure. The Screening Visit Form will still be completed, entering "Not Done" for
 testing not finished. A Final Status Form will be completed, and the reason for screen failure will
 be noted.

#### 477 **2.4 Genetic Screening Phase**

Participants passing the initial screening and enrolling into the Genetic Screening Phase will

submit their genetic lab reports for CGA review. The schematic of study design at the beginning

480 of the protocol summarizes the flow of the Genetic Screening Phase. Reference the GYROS

## 481 **Clinical Site Manual of Procedures** for detailed procedures.

All genetic reports will be uploaded to the FFB study website by the clinical site. These reports

483 may be reviewed by the CC, associated clinical site, Central Genetics Auditor (CGA), Genetics

484 Committee, and investigators involved in the oversight of the study (which includes the study

chair, Operations Committee, and Executive Committee). All genetic reports will be de-

identified and redacted of all personal data prior to uploading on the FFB study website.

487 The clinical site will upload supporting genetic documentation, including the genetic reports, on

the FFB study website. The CGA will review the genetic documentation provided by the clinical

site to verify the genetic screening data entry and appropriate documentation of the **Genetic** 

490 Screening Criteria. Additional documentation may be requested as needed to verify the Genetic

491 Screening Criteria and all genetic screening assessments.

- 492
   493 If Genetic Screening Criteria are verified, then the participant will be considered enrolled into the study cohort.
- 494
   495
   If the final study cohort is not verified, then the participant will be a genetic screen failure.

## 496 **2.4.1.1 Genetic Screen Failures**

Participants who do not meet criteria to continue in the study will be discontinued as a genetic
screen failure. A Final Status Form will be completed, and the reason for screen failure will be
indicated.

## 500 **2.4.1.2 Genetics Committee Review**

A Genetics Committee will review the genetic documentation of participants with verified **final study cohort criteria** and **enrolled into the study cohort** for interpretation and evaluation of whether the *OAT* mutations are causative of the disease (i.e., pathogenic, likely pathogenic). Cases that are not confirmed as disease causing will remain in the study and will not be considered ineligible. However, their data may be analyzed separately from those with

506 pathogenic mutations.

## 507 2.5 Final Study Cohort Criteria

- 508 The Final Study Cohort Criteria is participants that **meet one of the Genetic Screening**
- 509 Criteria, and have the genetic criteria confirmed by a Central Genetics Auditor (CGA).

- 510 Participants that meet the initial screening and eligibility criteria, who complete the Genetic
- 511 Screening Phase, and who meet the **final study cohort criteria** will be considered **enrolled into**
- 512 **the study cohort**. These participants should complete the natural history study.

513

#### 514

# **Chapter 3: Baseline Visit**

#### 515 **3.1 Baseline Visit**

- 516 Participants meeting criteria to enter the natural history study will return for a Baseline Visit
- 517 within sixty (60) days after receiving confirmation of meeting **final study cohort criteria** from 518 the CGA.
- 519
- 520 The Baseline Visit date will be documented as the date testing procedures began. All Baseline
- 521 Visit testing procedures will be completed within ten (10) days of the Baseline Visit date, unless
- 522 specified below.

#### 523 **3.2 Food Record and Blood Sample Collection**

524 All participants will complete the food record and blood sample collection as described below.

525	(1) Participant Contact
526 527 528 529	
 
The Clinical Site Coordinator will contact the participants (via phone or other remote interface) four (4) to ten (10) days prior to the first of the two (2) scheduled sample collection date. The Pre-Sample Collection Telephone Call will include instructions and reminders of:
 

530	$\circ$ The two (2) sample collection dates.
531	
 
Fasting instructions.
 

532	
 
Food record collection instructions.
 

533	(2) Food Record
534 535	
 
The participant will complete a food record to document their daily consumption during the following period:
 

536	• Begin three (3) days prior to the first sample collection date
537	• End one (1) day prior to the last sample collection date
538 539 540	
 
The participant will digitally send (e-mail or text) a picture of the food record documentation and either mail the original food tracking record to the site or bring it to the site at their Baseline Visit.
 

541 542	
 
The Clinical Site Coordinator will enter the data from the food record on the FFB Study Website.
 

543 544 545	
 
A Central Dietitian Reviewer (CDR) will review food record on FFB Study Website to determine nutritional content. This information will be documented on the FFB Study Website.
 

546	(3) Sample Collection
547	
 
Site Personnel will collect the following:
 

548 549	• Two (2) fasting plasma samples on two (2) different days, within ten (10) days of the Baseline Visit date.

550 551		• One (1) fasting blood spot fingerstick on the same day as one of the fasting plasma samples.
552 553		
 
All samples will be shipped to the Kennedy Krieger Institute (KKI).
 

554 555 556		
 
The Clinical Site Coordinator would request the most recent lab records with an albumin result if the participant indicated they are currently on an arginine- restricted diet.
 

557	3.3 Basel	ine Procedures
558 559 560 561 562 563	detailed in and certif	wing procedures will be performed at the Baseline Visit. The testing procedures are in the GYROS Clinical Site Manual of Procedures . An overview of the equipment fication requirements for all testing is in Chapter 5.1: Study Procedure nents . All ocular testing will be performed in each eye, OD first and then OS. Baseline es will last approximately seven $(7) - eight (8)$ hours. Baseline procedures will span 10) days.
564	3.3.1	Baseline Data Collection and Testing Cohorts 1 & 2
565	1.	Medical updates to include:
566		• New or changed adverse events (AEs)
567		New ocular procedures
568		New or changed medications
569		• Request medical records and laboratory records if applicable.
570	2.	Patient Reported Outcomes
571		
 
Adults: PROMIS®-29, MRDQ, ViSIO-PRO
 

572		
 
Adolescents: LPV-FVQ II, ViSIO-PRO
 

573		Children: LPV-FVQ II
574 575 576		• The PROs may be completed in person or remotely (phone or other remote methods) any time within six (6) months of the Baseline Visit (not required to be the same day as the rest of the Baseline Visit).
577	3.	Skin biopsy (3mm punch skin biopsy)
578		• Ship to Johns Hopkins University Department of Genetic Medicine Research Lab
579	4.	Spectral Domain Optical Coherence Tomography (SD-OCT)
580		Volume Scan
581		Vertical and Horizontal Scan
582	5.	Axial Length and Corneal Curvature Measurements
583	6.	Fundus Autofluorescence
584	7.	Widefield color photo

585	8. Optical coherence tomography angiography (OCTA)
586	• Ancillary test; may be waived with approval from the Coordinating Center
587	9. Red reflex photo
588	10. Full field Stimulus Threshold (FST)
589	11. Static perimetry
590 591	• Two (2) tests will be performed. The clinical site will compare the certified technician determined mean sensitivity from test one (1) versus test two (2).
592 593 594 595	
 
(a) If the absolute value of the difference between the two tests is ≤ 2.4 dB, then the participant passes static perimetry reliability criteria. A third test is not needed.
 

596 597 598	(b) If the absolute value of the difference between the two tests is > 2.4 dB, then the participant does not pass static perimetry reliability criteria. A third test will be required .
599	12. Fundus guided microperimetry
600 601	• Two (2) tests will be performed. The clinical site will compare the certified technician determined mean sensitivity from test one (1) versus test two (2).
602 603 604 605 606	(a) If the absolute value of the difference between the two tests divided by the average between them is $\leq 50\%$ OR the absolute value of the difference between the two tests is $\leq 0.5$ dB, then the participant passes the microperimetry reliability criteria. A third test is not needed .
607 608 609 610	(b) If the absolute value of the difference between the two tests divided by the average between them is $> 50\%$ AND the absolute value of the difference between the two tests is $> 0.5$ dB, then the participant does not pass microperimetry reliability criteria. A third test will be required .
611	13. Measurements to include:
612	
 
Weight
 

613	♦ Height
614	3.3.2 Baseline Data Collection and Testing Cohort 3
615	1. Medical updates to include
616	• New or changed adverse events (AEs)
617	New ocular procedures
618	
 
New or changed medications
 

619	• Request medical records and laboratory records if applicable.
620	2. Patient Reported Outcomes
621	
 
Adults: PROMIS®-29, MRDQ, ViSIO-PRO
 

